18.7 Instructions for PPD Requisition Form

Instructions for filling out the PPD Requisition Form.

Every PPD/ADA specimen submission must include a copy of the PPD Requisition Form. This form is supplied along with the kit. In addition, PPD will send you a copy of their Laboratory Manual.

Subject Information Section	
Site Number:	Fill in the NCI code for your institution. In addition, PPD requires that you add leading zeros so that all 10 spaces are filled. Do not leave any blank spaces or it will delay processing of your specimen. For example, if your NCI code is CA006, then you would enter "00000CA006" in this field.
Patient ID:	Enter the 6-digit SWOG patient identification number assigned at registration.
Year of Birth:	Enter all 4 digits of the patient's year of birth. For example, "1976".
Gender:	Place a mark in the appropriate box.

Below is an example of how this would look:

Visit Information Section

PK and ADA sampling should be done based on the treatment cycles for pembrolizumab, not on calendar weeks. However, PPD has created visit labels assuming that there will be no treatment delays or variation in schedule. The following table is intended to help you pick the most appropriate visit label for your PK/ADA specimen submission:

Visit Label	Specimen to be submitted
Week 1	Sample collected prior to the first infusion on Cycle 1
Week 4	Sample collected prior to the second infusion during Cycle 1.
Week 10	Sample collected prior to the second infusion during Cycle 2
Week 19	Sample collected prior to the third infusion on Cycle 3
Week 25	Sample collected prior to the first infusion on Cycle 4
Week 49	Sample collected prior to the infusion on Cycle 6
Post Treatment FU 30 Days	Sample collected 30 days after discontinuation of pembrolizumab (provided patient has not started a new anti-cancer therapy prior to this time)
Unscheduled	PPD has provided 10 “unscheduled visit” labels. These should be used sparingly if at all. Using the guide provided above, you should be able to identify the correct visit label for your submission.

18.8 Translational Medicine: Retrospective T-Cell Receptor Beta Chain (TCR β) Sequencing of Banked Samples from S1404

a. Objectives

1. Primary: To evaluate the association between TCR β variable gene (TRBV) haplotype and Grade 3-4 immune-related adverse events (irAEs) among Stage III melanoma patients treated with adjuvant Ipilimumab or Pembrolizumab.
2. Secondary: To describe the TRBV haplotype distribution among this cohort of patients studied.
3. Secondary: To assess associations between baseline patient demographics and TRB haplotype.

b. Background

Checkpoint blockade immunotherapy (CPI) can elicit anti-cancer T cell responses mediating durable progression free survival but may also promote T cell destruction of healthy tissue to elicit irAEs. Efforts to identify germline variants associated with irAEs using whole genome sequencing (WGS) or microarrays have yet to reveal markers predictive of adverse events following immunotherapy. Identifying such biomarkers could allow for personalized drug selection and dosing to ultimately enable safer and more effective immunotherapy, particularly in light of the increasing use of combination CPI regimens having a significant incidence of severe adverse events.⁽¹⁾

Despite previous efforts, three lines of reasoning support the notion that germline encoded TRBV polymorphism could be a key determinant of adverse events during CPI. First, the TCR locus is repetitive and structurally complex, impeding the measurement of variation by traditional short read WGS or microarray-based methods.⁽²⁾ Second, single amino acid substitutions within the framework or complementarity-determining region (CDR) 1 and 2 regions of the rearranged TCR β chain are known to significantly alter TCR affinity for human leukocyte antigen (HLA).⁽³⁾ Third, adverse events during immunotherapy may manifest as acute versions of chronic autoimmune diseases (i.e. fulminant type 1 diabetes) that have been separately linked to TRBV polymorphism.⁽⁴⁾ To circumvent the challenge in measuring TRBV polymorphism by WGS, Thermo Fisher has developed a cost-efficient and rapid method for detection of TRBV polymorphism by next-generation sequencing (NGS) of rearranged TCR β chains from peripheral blood leukocytes.⁽⁵⁾ Based on current knowledge, this represents the first NGS-based method to permit haplotype-level resolution of the TRB locus.

A pilot study involving haplotype analysis of the TRB locus by TCR β sequencing was previously conducted at the University of Texas MD Anderson Cancer Center (MDACC) under the PI, [name], using the peripheral blood of 81 Caucasians who had graded adverse events following immunotherapy. The results of this analysis revealed the presence of 6 major haplotype groups within the study cohort. Strikingly, members of one haplotype group, accounting for 33% of patients, appear to be protected against severe (Grade 3-5) adverse events (0% frequency) while 14% to 44% of patients in other haplotype groups had severe adverse events ($p=7.1E-4$, Fisher's 2x2 exact test). Should this finding be confirmed in the larger SWOG cohort, this would indicate that TRBV allele profiling may serve as a predictive biomarker for adverse events to enable personalized checkpoint blockade drug selection and dosing.

c. Experimental Research Technique

Baseline banked blood samples from Caucasian patients on **S1404**
Preferred source of sample: buffy coat

Total RNA extracted from PBL or whole blood will be used as input for TCR β sequencing using the Thermo Fisher Scientific product Oncomine TCRB-LR (SKU A35386). This assay utilizes a long-amplicon approach (up to 400 bp) to capture the sequences of all 3 CDR regions of the TCR Beta chain. Sequencing assays for up to 240 patients (details of patient selection provided in the statistical section) will be performed at Thermo Fisher. Results from the haplotype analyses will be provided to the PI, [name] and the SWOG Statistical Center. This protocol will allow for extraction of both DNA and RNA from the cryopreserved cell pellets. Total RNA will then be used for TCRB-LR library preparation at Thermo Fisher.

d. Statistical Plan

Sample selection: the pilot haplotype work has been in Caucasian patients, so we will use baseline blood samples from Caucasian patients enrolled on **S1404**. We note that melanoma incidence is higher among Caucasian patients than other races, and 95% of patients enrolled on **S1404** were Caucasian. In addition, we will restrict analyses to the subset of patients who planned to receive Ipilimumab as their control arm regimen prior to randomization. First, we will analyze 120 patients who were randomized to the control arm and treated with Ipilimumab on **S1404**; we will select 60 patients with Grade 0-2 irAEs and 60 patients with Grade 3-4 irAEs (selection will be random among all patients with appropriate consent who have baseline samples meeting these criteria [>150 patients available for each irAE cohort]). We note that the Grade 3-4 irAE rate is 35% among patients treated with Ipilimumab on the control arm. We chose to over-sample Grade 3-4 irAE because the incidence of haplotype 2 among this subset is expected to be small, and we want adequate power to evaluate the incidence (further details of expected incidence below in the primary analysis section). If the pilot data results are validated among these Ipilimumab patients (details of primary analysis below), we will select 120 patients randomized and treated with pembrolizumab; we will select 60 patients with Grade 0-2 irAEs and 60 patients with Grade 3-4 irAEs (selection will be random among all patients with appropriate consent who have baseline samples meeting these criteria [>150 patients available for each irAE cohort]). We note that the Grade 3-4 irAE rate is 15% on the pembrolizumab arm.

Primary analysis: TRBV haplotype analysis will be performed as described in Looney et al. (at Thermo Fisher) and the results of the analysis will be provided to [name] and the SWOG statistical center. The association between haplotype Group 2 and the incidence of severe Grade 3-4 adverse events will be assessed using Fisher's exact test; haplotypes 1, 3, 4, 5, 6 will be grouped together for this analysis (i.e., we will compare haplotype 2 versus all other haplotypes). (6) In the pilot data, the haplotype 2 incidence was 33%. We assume the Grade 3-4 irAE to be 12% among haplotype 2 patients (was 0% in the pilot data) and to be 46% among other haplotype patients. Given these incidence assumptions, we expect that 11% ($0.33*0.12/ (0.33*0.12+0.67*0.46)$) of patients with a Grade 3-4 irAE in the Ipilimumab cohort of **S1404** will be haplotype 2, and that 89% will have another haplotype. Similarly, we expect that 43% ($0.33*0.88/ (0.33*0.88+0.67*0.54)$) of patients with a Grade 0-2 irAE in the Ipilimumab cohort of **S1404** will be haplotype 2, and that 92% will have another haplotype. With 60 patients with Grade 3-4 irAE and 60 patients with Grade 0-2 irAE, under these assumptions Fisher's exact test has 92% power with a two-sided alpha of 5%.

If a significant association between haplotype 2 and Grade 3-4 irAE is observed in the Ipilimumab cohort, we will process samples on the 120 Pembro patients and perform the same analysis (Fisher's exact test with two-sided alpha = 5%). If we assume the same incidence of haplotype 2 (33%), and that 2% of the Grade 3-4 AE cohort will be haplotype 2, this test has 86% power.

Secondary analysis: Associations between haplotype and baseline patient characteristics (age, performance status, stage, primary tumor characteristics, LDH) will be evaluated using Fisher's exact test and Wilcoxon-rank sum tests.

Analyses and interpretation of data output will be completed within 1 year of the receipt of specimens.

e. Data Analysis

The data will be analyzed by the SWOG Statistics and Data Management Center ([name].). The Haplotype Analysis will be performed by Thermo Fisher ([name]).

f. Specimen Information

Laboratory Performing Analysis:

The University of Texas MD Anderson Cancer Center
[name] (c/o [name])
The University of Texas MD Anderson Cancer Center
Investigational Cancer Therapeutics
[name]
[name]
[contact]

Thermo Fisher Scientific:

[name]
Thermo Fisher Scientific
[name]
[contact]
[contact] | thermofisher.com

Specimens used:

Preserved frozen pelleted peripheral blood leukocytes (PBL), peripheral blood mononuclear cells (PBM) are highly preferred, though whole peripheral blood is also acceptable.

2 ml of whole peripheral blood, from which peripheral blood leukocyte (PBL) total RNA will be extracted in the laboratory of Thermo Fisher. 50 ng of PBL RNA will be used for library preparation and sequencing via the Oncomine TCRB-LR assay.

Baseline (pretreatment) samples are highly preferred, though any timepoint is acceptable.

g. References

- 1 Larkin, J et al. Combined Nivolumab and Ipilimumab or monotherapy in untreated melanoma. NEJM 373:23-34, 2015.

- 2 Watson, C et al. Comment on 'A database of human immune receptor alleles recovered from population sequencing data'. *J Immunol* 198:3371-3373, 2017.
- 3 Robbins, P et al. Single and dual amino acid substitutions in TCR CDRs can enhance antigen-specific T cell functions. *J Immunol* 180:6116-6131, 2008.
- 4 Pierce, B et al. The missing heritability in T1D and potential new targets for prevention. *J Diabetes Res* 737485, 2013.
- 5 Looney, T et al. Haplotype analysis of the TRB locus by TCRB repertoire sequencing. *bioRxiv* 406157, 2018.
- 6 Looney, T et al. Haplotype analysis of the TRB locus by TCRB repertoire sequencing. *bioRxiv* 406157, 2018.

18.9 Instructions for the SWOG Biospecimen Bank - Lab #201, Solid Tissue, Myeloma and Lymphoma Division

a. **General Banking Instructions**

The SWOG Biospecimen Bank will store formalin-fixed paraffin-embedded (FFPE) tissue blocks or slides at room temperature.

Aliquots of frozen, processed plasma, buffy coat, and serum are banked in -80°C freezers for long-term storage.

b. **Instructions Related to RNA Extraction and T-Cell Receptor Beta Chain (TCR β) Sequencing (Appendix 18.8)**

The SWOG SDMC will provide a list of patients and time points to the Bank for distribution to Thermo Fisher. For each patient, the Bank will ship 1 vial of frozen buffy coat (from Baseline time point, if possible) on dry ice for RNA extraction and T-Cell Receptor Beta Chain (TCR β) Sequencing.

c. **Instructions Related to circulating tumor DNA (ctDNA) (Appendix 18.10)**

The SWOG SDMC will provide a list of patients and time points to the Bank for distribution to the Natera laboratory. For each patient, an H&E slide from the primary tumor or lymph node metastasis will be scanned to a 40X digital image for digital pathology review by [name], who will provide specimen quality data (e.g., %tumor vs. necrosis, %tumor vs. normal, confirmation of concordance with institutional diagnosis, and comments when applicable) and will digitally annotate slides, as needed, for specimens that will require macrodissection to enrich tumor content. Following pathology QA review, the Bank will either scrape unstained slides (macrodissected as needed), or section FFPE blocks. All tissue will undergo co-extraction for DNA and RNA.

DNA will be extracted from buffy coat from one time point for each patient.

All nucleic acids will undergo quantitation and QC before storage in a -80°C freezer.

For each patient, the Bank will ship the following specimens to Natera on dry ice for overnight delivery:

- At least 500 ng DNA from primary tumor or lymph node metastasis and DNA from buffy coat
- A minimum of 4 ml of frozen plasma from Baseline
- A minimum of 4 ml of frozen plasma at start of cycle 3
- A minimum of 4 ml of frozen plasma at start of cycle 4
- A minimum of 4 ml of frozen plasma at removal from protocol therapy or relapse

18.10 Translational Medicine: Association of Circulating Tumor DNA (ctDNA) with Relapse-Free Survival in High-Risk, Resected Melanoma Patients

a. Objectives

1. Primary (integrated): To evaluate associations between pretreatment ctDNA (present versus absent) and relapse within 2 years of randomization in a case-control analysis across treatment arms
2. Secondary (integrated): To evaluate associations between pretreatment ctDNA and relapse within 2 years of randomization in a case-control

analysis within each treatment arm (after treatment arm data are unblinded to investigators).

3. Secondary (integrated): To evaluate associations between “early-on treatment” ctDNA levels and relapse within 2 years of randomization
4. Secondary (integrated): To describe ctDNA levels at end of therapy and time of relapse

b. Background

From a double-blind, randomized, placebo-controlled trial, Eggermont, AMM et al. reported improved relapse free survival with adjuvant pembrolizumab in high risk, resected, Stage III melanoma patients compared to placebo. Specifically, pembrolizumab therapy was associated with a one-year rate of recurrence-free survival of 75.4% [95% confidence interval CI, 71.3 to 78.9] vs. 61.0% [95% CI, 56.5 to 65.1] in the placebo cohort. Thus, while anti-PD-1 therapy reduces the risk of disease progression of Stage III melanoma, 25% of patients are predicted to relapse within 1-year. For those untreated, up to 39% will relapse. At present, there are no biomarkers available to predict which of these patients are most likely to relapse. Improving outcomes for these patients in the future will require significant advancements in risk stratification tools.

The Signatera test, offered by Natera, is an emerging biomarker that has shown promising clinical utility for the detection of minimal residual disease and early detection of relapse. (1, 2, 3, 4) The assay quantifies cell free, circulating tumor DNA (ctDNA) present in plasma, down to a 0.1% mutant allele fraction. In patients with non-small cell lung cancer, colorectal cancer, muscle-invasive bladder cancer and breast cancer, studies with Signatera have shown an unprecedented positive predictive value (PPV) for relapse ranging from 93%-100% with an average lead time of 2.8-9.5 months compared to radiographic detection. (5, 6, 7, 8)

The **S1404** Stage III melanoma cohort includes post-operative plasma samples collected prior to the initiation of immunotherapy. With these samples, we may be able to discern if baseline ctDNA levels can risk stratify patients. The overall goal is to determine if highly sensitive, tumor-guided ctDNA testing can distinguish **S1404** patients who remain disease free from those who have relapsed. We hypothesize that the Signatera test results will be associated with relapse outcomes in the trial (and within each treatment arm) and that nondetectable ctDNA levels will be associated with lack of relapse within 2 years. For patients who have detectable ctDNA at time zero, we hypothesize that reduction in ctDNA levels will be associated with a lack of relapse within 2 years.

c. Experimental Research Technique

The Natera Signatera assay is a personalized medicine approach for cancer patients that allows for serial testing of peripheral blood for monitoring of minimal residual disease and molecular relapse. Sixteen patient tumor-specific, somatic, non-driver mutations are selected based on exome sequencing comparisons of germline (buffy coat) to tumor (FFPE tissue). Through a proprietary algorithm, Natera chooses truncal, founder mutations that persist throughout the clonal phylogeny of the heterogeneous tumor population. Each patient plasma sample is then tested with a custom-designed assay that quantifies the 16 unique somatic mutations. For this study, germline and tumor exome data files will be provided to SWOG for future studies.

[name] (PI) is board certified in both Anatomic Pathology and Molecular Genetic Pathology. She is a Medical Director of Molecular Oncology at ARUP Laboratories, a national reference laboratory owned by the University of Utah, where she oversees the design, validation and routine clinical testing of a

variety of molecular, genomic and immunohistochemical clinical assays, including ctDNA assays. She is an independent investigator at the Huntsman Cancer Institute (Department of Pathology, University of Utah), with an NCI and American Cancer Society-funded melanoma research laboratory. She is Co-Director of the Biospecimen Pathology Core for the HCI Melanoma SPORE initiative. She is a quality control anatomic pathologist for HCI Biorepository – providing histomorphologic review of melanoma and sarcoma tumor banking. [name] is ideally suited to lead this study.

d. Statistical Plan

The case-control pairs will be selected randomly among eligible patients with all required samples. Cases will be patients who relapsed within 2 years of randomization. Controls will be patients who were alive without relapse for at least 2 years after randomization. To the degree possible with the sample sizes available, case-control patients will be matched based on the randomization stratification factors stratification factors stage (stage IIIA and IIIB versus IIIC and IV) and PD-L1 status (positive versus negative versus indeterminate). Also, to the degree possible with the sample sizes available, we will restrict to patients who received ipilimumab on the control arm, and restrict to patients on the pembrolizumab arm who declared before randomization that they would have received ipilimumab if randomized to the control arm.

With 100 total patients, 50 cases and 50 controls, and assuming 24% of control patients (no relapse or death within first two years) have detectable baseline ctDNA levels, we will have 90% power with a two-sided alpha of 5% to detect an odds ratio (OR) of 5.3 or more extreme if the correlation between cases and controls is 0.5. If the correlation is lower than 0.5, we have additional power. For example, if the correlation is 0.2, we have 90% power to detect an OR of 4.26 or more extreme.

For secondary analyses we will:

- evaluate baseline ctDNA as a quantitative covariate in a conditional logistic regression model,
- evaluate associations between presence/absence of ctDNA and quantitative ctDNA levels at the third and fifth cycles and relapse within 2 years using conditional logistic regression and landmark analyses,
- descriptively summarize changes in ctDNA levels over time using descriptive statistics including means, medians, and inter-quartile ranges and spaghetti plots
- perform all the above analyses within each treatment arm, and fit regression models with a treatment arm interaction covariate (to be performed after results by treatment arm from the trial are released by the DSMC).

No information on arm label will be provided during the processing, labeling, or analyses of this project until the DSMC releases results of the trial.

Analyses and interpretation of data are planned to be completed within 1 year of the receipt of specimens.

e. Data Analysis

Natera will report ctDNA levels to SWOG Statisticians. SWOG statisticians will perform all analyses linking ctDNA results with patient-level data.

f. Specimen Information

Exome sequencing and ctDNA detection will be performed by Natera and statistical testing will be performed by SWOG statisticians ctDNA and outcome correlation data will be reported to [name] (PI).

The SWOG Biospecimen Bank - Lab #201 will ship the following specimens to Natera on dry ice for overnight delivery as outlined in Section 18.9.c:

- 1) DNA from FFPE tumor
- 2) DNA from germline (buffy coat)
- 3) frozen plasma aliquots

Natera
[name]

Natera study contact:
[name], MBA (Medical Director, Oncology)
[contact]
[contact]

Specimens used:

Eligible patients who received ipilimumab or pembrolizumab on **S1404**. This proposal requires:

- primary tumor or lymph node metastasis AND plasma AND buffy coat from baseline,

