11.7 Analyses of other objectives

- a. **Estimation of OS and RFS in PD-L1 negative subgroup:** Cox regression models will be used to estimate hazard ratios and calculate confidence intervals to compare treatment arms in the PD-L1 negative subgroup. In addition Cox regression models for OS and RFS will be used to estimate interaction terms between PD-L1 status and treatment arm.
- b. **Analysis of toxicity:** On the MK-3475 (pembrolizumab) arm, six hundred and twenty eligible patients will be sufficient to estimate toxicity rates within $\pm 4\%$ (95% confidence interval). Any toxicity occurring with at least a 0.8% probability is likely to be observed at least once (99% probability). Assuming that on the Control Arm 310 patients receive HD-IFN and 310 patients receive ipilimumab, this will be sufficient to estimate toxicity rates for these regimens to within $\pm 6\%$ (95% confidence interval). Under this assumption any toxicity occurring on a particular control arm regimen with at least a 1% probability is likely to be observed at least once (96% probability).
- c. **Analysis of post-relapse therapy:** Data on therapy after relapse will be collected for three years after relapse (or until 10 years after registration maximum). Therapies will be categorized into one of two categories: systemic or local. Specific therapies after relapse will be tabulated and summarized. Therapy after relapse will be analyzed as a time-dependent variable in Cox regression analyses for the endpoint of OS after relapse.
- d. **Analysis of BRAF mutation data:** Prestudy BRAF mutation status on patients will be collected. BRAF mutation status will be analyzed as a covariate in Cox regression analyses and exponential-logistic cure regression models. (26) In addition, the interaction between BRAF mutation status and treatment arm will be

analyzed in Cox regression models and in exponential-logistic cure regression model.

- e. **Analysis of long-term survivors/cured patients:** Exponential-logistic cure regression models will be used to examine the association between known prognostic factors (including stage) and long-term survivor/cure status, and survival for patients who are not long-term survivors/cured. (27)
- f. **Other analyses of OS and RFS:** A restricted mean survival time analysis will be done as a supportive analysis.

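### Appendix 18.8 counts more than 150 pembrolizumab patients with Grade 3-4 irAEs, which its own 15% rate cannot supply; whether the 60 it needs exist is uncertain

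*Combined protocol and SAP*

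**What the plan says.** Appendix 18.8, part d, selects two cohorts in sequence. The first has 120 ipilimumab-treated control-arm patients, 60 with Grade 0-2 and 60 with Grade 3-4 irAEs. If the haplotype association is significant there, a second cohort of 120 pembrolizumab patients is taken in the same way, pairing a lower-grade group of 60 with the cases: "and 60 patients with Grade 3-4 irAEs (selection will be random among all patients with appropriate consent who have baseline samples meeting these criteria". Both cohort descriptions carry the same bracket, ">150 patients available for each irAE cohort".

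The rates stand beside these counts. For the first cohort: "We note that the Grade 3-4 irAE rate is 35% among patients treated with Ipilimumab on the control arm". For the second: "We note that the Grade 3-4 irAE rate is 15% on the pembrolizumab arm".

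The pool is narrowed in two further ways. Only Caucasian patients are used (the appendix gives them as 95% of enrolment), and the plan will "restrict analyses to the subset of patients who planned to receive Ipilimumab as their control arm regimen prior to randomization". Banking is optional for patients (Section 15.3).

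**The concern.** The same availability figure is given for two cohorts whose Grade 3-4 rates differ by more than a factor of two. It is plausible at 35%. At 15% it implies an arm far larger than the trial was designed to have.

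The figure matters because it is the only evidence in the appendix that 60 qualifying pembrolizumab cases can be found. The text has no rule for fewer than 60, so if the pool is short, someone will have to decide which criterion to relax after the ipilimumab result is known. The reach is limited: this is a conditional, retrospective sub-study listed under Other Objectives (Section 1.4), and no trial endpoint depends on it.

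**Working it through.** **Inputs**
- Planned total: 1,378 registered, 1,240 eligible (Section 11.1).
- Allocation 1:1, with planned control regimen as a stratification factor (Section 6.0).
- Pembrolizumab arm: 620 eligible (Section 11.7b). Upper figure: 1,378 / 2 = 689, which treats every registered patient as randomised.
- Grade 3-4 irAE rates: 15% pembrolizumab, 35% ipilimumab (Appendix 18.8d).
- Caucasian share: 95% (Appendix 18.8d).
- Share declaring ipilimumab: not reported. Section 11.7b uses one half: "Assuming that on the Control Arm 310 patients receive HD-IFN and 310 patients receive ipilimumab".
- Actual enrolment and banking consent rate: not given.

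**Step 1. Can the stated figure be reproduced?**
Arm size needed for more than 150 cases: 151 / 0.15 = 1,007.
Expected cases with no restriction at all: 0.15 x 620 = 93; 0.15 x 689 = 103.
Rate that would be needed instead: 151 / 689 = 21.9%; 151 / 620 = 24.4%.
Binomial chance of more than 150 cases at 15%: 9e-7 for n = 689; 7e-10 for n = 620.
The figure is not reproduced at either arm size.

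**Step 2. Are there 60 after the plan's own restrictions?**
Expected cases = arm size x 0.15 x 0.95 x share declaring ipilimumab, with full consent and samples.

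| Share declaring ipilimumab | Arm = 620 | Arm = 689 |
|---|---|---|
| 50% (Section 11.7b) | 44 | 49 |
| 60% | 53 | 59 |
| 70% | 62 | 69 |
| 80% | 71 | 79 |

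Share needed for 60 cases: 60 / (689 x 0.15 x 0.95) = 61%; 60 / (620 x 0.15 x 0.95) = 68%.
If 70% to 90% consent to banking (an assumption), the 50% row falls to 31-40 (arm of 620) or 34-44 (arm of 689).

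**Step 3. A check that does not need the 50:50 assumption.**
Suppose the ipilimumab bracket is correct. Then at least 151 / 0.35 = about 432 control-arm patients meet the race, regimen, consent and sample criteria. Because planned regimen is a stratification factor, a similar number should qualify on pembrolizumab. Expected Grade 3-4 cases: 432 x 0.15 = about 65. The binomial chance of fewer than 60 is about 24%. Since the bracket is a lower bound, 65 is the count if it is only just met.
This scenario implies that 432 / 689 = 63% to 432 / 620 = 70% of the control arm qualify. At 50:50 the ipilimumab bracket would itself fail: 310 x 0.35 = 109.

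**Step 4. Would a shortfall matter for power?**
Exact power of Fisher's test, two-sided 5%, with 60 Grade 0-2 controls. The plan assumes 2% haplotype 2 among Grade 3-4 cases. For controls I used 33%, and also (0.33 - 0.15 x 0.02) / 0.85 = 38.5%, which applies if 33% is meant as the incidence in the whole arm.

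| Grade 3-4 cases | 2% vs 33% | 2% vs 38.5% |
|---|---|---|
| 60 | 99.8% | >99.9% |
| 49 | 99.8% | >99.9% |
| 44 | 99.6% | >99.9% |
| 30 | 98.0% | 99.7% |

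The plan states 86% for 60 versus 60. That is not reproduced under either reading. Under the weaker contrast the plan expects for ipilimumab (11% vs 43%), 44 cases give 96% and 30 give 89%.

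**The case against.** The best counter-argument concerns the second half. The 50:50 split in Section 11.7b is a pre-trial assumption made to size toxicity intervals. Appendix 18.8 was evidently written with trial data in hand, since it reports observed rates and the racial make-up of those enrolled. Its own ipilimumab count points to a larger ipilimumab share and to about 65 pembrolizumab cases, enough for the design. This stands, and it is why 44 to 49 is one scenario and not the expected number. It depends, though, on a bracket whose twin is shown to be wrong, and 65 leaves little margin.

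The sample filter is also softer than part d suggests. Part f of the same appendix accepts any timepoint, and Appendix 18.9b asks for baseline where possible. That may recover some patients, but it cannot lift 93 to 103 above 150. Part c sets sequencing at up to 240 patients, a ceiling that leaves room for fewer, and Fisher's test does not need equal groups.

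A reader might infer three stronger things that the documents do not support:
- **That more than 150 is impossible outright.** Actual enrolment is not stated. The conclusion is that the figure cannot be reconciled with planned enrolment; rescuing it would take over 1,000 patients on one arm.
- **That the pembrolizumab cohort cannot be assembled.** The scenarios fall on both sides of 60.
- **That using every available case, in place of a random draw, biases the comparison.** A census of qualifying cases adds no selection bias over a random sample from the same cases.

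**Conclusion.** The availability figure for the pembrolizumab Grade 3-4 cohort is wrong as written: more than 150 stated, against about 93 to 103 expected before any restriction. This rests on the planned arm size of 620 to 689 and the appendix's own 15% rate. The bracket repeats the ipilimumab sentence and may have been carried over, but that is inference.

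Whether 60 cases exist is open: about 44 to 49 at the 50:50 split, and about 65 if the ipilimumab bracket holds. Both scenarios apply the arm-wide 15% to patients who declared ipilimumab. The first is before consent and sample losses; the second assumes the arms do not differ in consent, samples or starting treatment.

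The consequence is minor. A shortfall would mean the cohort cannot be filled as written, but under the plan's 2% versus 33% assumption power stays at 98% or more with 30 or more cases. The stated 86% needs correcting in any event.

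**What to change.** In Appendix 18.8d:
1. Replace the bracket for the pembrolizumab Grade 3-4 cohort with the actual number who meet the race, planned-regimen, consent and sample criteria. Confirm the ipilimumab figure in the same query.
2. Add one sentence: all qualifying Grade 3-4 pembrolizumab patients up to 60 will be used, with 60 Grade 0-2 controls.
3. Restate the power for that number of cases, naming the haplotype 2 proportion assumed in each group.
4. Say whether non-baseline samples count, so that parts d and f agree.

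The cost is one database count and a few sentences in the appendix. Trial conduct and the primary analyses are unaffected.

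### Appendix 18.8, part d: the Grade 0-2 haplotype split and both power figures (92% and 86%) do not follow from the printed inputs

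*Combined protocol and SAP*

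**What the plan says.** Appendix 18.8, part d, compares haplotype 2 with all other haplotypes between patients with Grade 3-4 and Grade 0-2 immune-related adverse events. The association "will be assessed using Fisher's exact test; haplotypes 1, 3, 4, 5, 6 will be grouped together for this analysis". Each cohort has 60 patients per grade group.

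**Ipilimumab cohort.** The inputs are the haplotype 2 prevalence ("In the pilot data, the haplotype 2 incidence was 33" percent) and the event rates by haplotype ("We assume the Grade 3-4 irAE to be 12% among haplotype 2 patients (was 0% in the pilot data) and to be 46" percent among the others). From these the plan expects 11% of Grade 3-4 patients "will be haplotype 2, and that 89% will have another haplotype". For Grade 0-2 patients it prints an expression given as 43%, followed by "will be haplotype 2, and that 92% will have another haplotype". It then states that, under these assumptions, Fisher's "exact test has 92% power with a two-sided alpha of 5" percent.

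**Pembrolizumab cohort.** This cohort is processed only if the ipilimumab association is significant. The same test is planned. The plan assumes the same 33% incidence of haplotype 2 and a 2% haplotype 2 share in the Grade 3-4 group, and states that "this test has 86% power". The sample-selection paragraph gives a Grade 3-4 event rate of 15% on this arm. No haplotype 2 share is stated for the Grade 0-2 group.

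**The concern.** The analysis has two categories, so the shares within a grade group must sum to 100%; 43% and 92% cannot both be right. Once one printed figure is impossible, the powers built on the same inputs need checking, and neither reproduces.

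The power statement justifies 60 per group and the over-sampling of Grade 3-4 patients, and it covers up to 240 banked samples. It is also what a reader would use to interpret a null result. As printed, nobody can tell which effect the substudy was sized to detect.

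**Working it through.** **Inputs, all from Appendix 18.8, part d.** Haplotype 2 prevalence 33%; Grade 3-4 event rate 12% with haplotype 2 and 46% otherwise; 60 versus 60; two-sided alpha 5%. For pembrolizumab: 33% incidence, 2% haplotype 2 among Grade 3-4 patients, 15% Grade 3-4 event rate.

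**Step 1. A figure that reproduces.** Haplotype 2 share among Grade 3-4 ipilimumab patients:

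0.33×0.12 / (0.33×0.12 + 0.67×0.46) = 0.0396 / 0.3478 = 11.4%, complement 88.6%.

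The plan prints 11% and 89%. The denominator, 34.8%, also agrees with the 35% event rate quoted for ipilimumab. The inputs are therefore coherent up to this point.

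**Step 2. The Grade 0-2 split.** By the plan's own expression:

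0.33×0.88 / (0.33×0.88 + 0.67×0.54) = 0.2904 / 0.6522 = 44.5%, complement 55.5%.

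The plan prints 43% and 92%, a sum of 135%. Even if 43% is kept, the complement is 57%.

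**Step 3. Power for each cohort.** Power is the sum, over all 61×61 possible tables, of Binomial(60, p1) × Binomial(60, p2) for those tables with a two-sided Fisher p-value of 0.05 or less.

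For pembrolizumab, 33% can be read as the Grade 0-2 share itself or as the overall prevalence. On the second reading the Grade 0-2 share is (0.33 − 0.15×0.02) / 0.85 = 38.5%.

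| Cohort and reading | Grade 3-4 share | Grade 0-2 share | Computed power | Stated power |
|---|---|---|---|---|
| Ipilimumab, printed shares | 11% | 43% | 97.5% | 92% |
| Ipilimumab, unrounded shares | 11.4% | 44.5% | 98.1% | 92% |
| Pembrolizumab, 33% as Grade 0-2 share | 2% | 33% | 99.85% | 86% |
| Pembrolizumab, 33% as overall prevalence | 2% | 38.5% | above 99.9% | 86% |

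**Step 4. Does another method explain the gap?** For ipilimumab, a one-sided Fisher test gives 98.9-99.2%, the uncorrected normal approximation 98.4-98.8%, and the continuity-corrected version 97.2-97.9%. Grouping by haplotype (40 versus 80, at 12% versus 46%) gives 98.0%. For pembrolizumab at 2% versus 33%, the normal approximation gives 99.7% and the continuity-corrected version 99.4%. None comes near 92% or 86%.

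**Step 5. Inputs that would give the stated powers.** These are back-calculated and do not show where the figures came from.

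- About 92% at 60 versus 60: 11% versus 38% gives 91.7%; 8% versus 33% gives 91.3%; 8% versus 34% gives 93.0%.
- About 86% at 60 versus 60: 2% versus 19.5% gives 86.1%. So does a Grade 3-4 share of 12% with the other printed inputs kept: (0.33 − 0.15×0.12) / 0.85 = 36.7%, and 12% versus 36.7% gives 85.6%.

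**The case against.** The strongest reply is that the printed powers may be right and an input misprinted. If the pembrolizumab 2% were meant as 12%, the remaining printed inputs give 85.6%, which rounds to the stated 86%; and 12% is close to the 11% used for ipilimumab. Likewise, the stray 92% is the complement of 8%, and 8% versus 33-34% gives 91-93% power. This stands as a possibility. It cannot be proved from the documents, but it means that one may not simply declare the powers wrong and the inputs right.

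A second reply is that the discrepancy does no harm. Under the printed inputs true power exceeds stated power, so 60 per group is enough. That also stands, on those inputs.

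Three stronger readings are tempting, and the documents do not support them.

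- **That power is definitely understated, by about 6 points (ipilimumab) and 14 points (pembrolizumab).** This holds only if the printed inputs are the intended ones.
- **That the step to the pembrolizumab cohort is compromised.** That step depends on an observed significant association, not on the power figure.
- **That 240 samples are being wasted.** The plan says up to 240, and the second 120 are conditional. It reports more than 150 patients available in each event group. Using fewer samples would be a design preference.

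**Conclusion.** The point holds as an internal inconsistency. The Grade 0-2 split is wrong whichever way the rest is resolved: its printed shares sum to 135%, and the plan's own expression gives 44.5% and 55.5%. Under the printed inputs the ipilimumab power is 97.5-98.1% against a stated 92%, and the pembrolizumab power is 99.85% or higher against a stated 86%. These results assume independent binomial sampling within each grade group and a two-sided exact test at 5% with 60 per group.

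Whether the inputs or the powers are in error cannot be settled from the documents. If the inputs stand, the error is conservative and the sample size adequate. In either case the test and its alpha are unaffected. This is a minor correction to a retrospective substudy listed under Other Objectives, and it has no bearing on the trial's primary endpoints.

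**What to change.** In Appendix 18.8, part d:

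1. Replace the Grade 0-2 split with 44.5% haplotype 2 and 55.5% other, if the 33%, 12% and 46% inputs stand.
2. Have the study statistician confirm inputs and power together for each cohort.
   - If the printed inputs are intended, restate power as about 98% for ipilimumab and above 99% for pembrolizumab.
   - If 92% and 86% are intended, correct the inputs to those that produce them, and recompute the split from the corrected inputs.
3. State the assumed haplotype 2 share among pembrolizumab Grade 0-2 patients, and say whether 33% is that share or the overall prevalence.

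The cost is appendix wording and a short recalculation. The sample selection and the test need not change if the printed inputs are confirmed.
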